Discovery of Effects of Retinol on Human Skin Aging in Individuals of East Asian Descent

Protocol and Statistical Analysis Plan

NCT02906566

October 12, 2016

[name], Principal Investigator Stanford University School of Medicine [name]

Title of Proposal:

Discovery of Rejuvenation Effects of Vitamin A (Retinol) Lotion on Naturally Aged Skin in an East Asian Cohort

Version 101216

Principal Investigator:

[name]
Stanford University School of Medicine
Assistant Professor, Department of Dermatology
[name]
[name]

Introduction

Increasing evidence from multiple organ systems suggests that there are different rates of natural aging in humans. One of the best organs to study human aging is the skin, due to its amenability to clinical inspection and serial biopsy. Recently, genome-wide analysis in an Ashkenazi population has provided the evidence that skin can age at different rates and that youthful appearing skin is associated with different gene variants (Chang *et al.*, 2014). The first studies to demonstrate anti-aging effects of a topical agent were published in 1988 in which topical tretinoin was used to improve the appearance in photo-aged skin (Weiss *et al.*, 1988). Subsequently, topical retinol (vitamin A) lotion was shown in a placebo-controlled study to decrease fine wrinkling in photo-protected skin in older individuals residing in nursing homes (Kafi *et al.*, 2007).

Recent advances in deep sequencing technology have enabled the unbiased and detailed analysis of gene expression changes in the skin (Chang *et al.*, 2013). Furthermore, a type of deep sequencing technique called 3'-end sequencing has demonstrated the ability to identify changes in a class of transcripts called long non-coding RNAs (Inc RNAs) that are now understood to be a previously unrecognized way to regulate gene expression. Here, we propose to utilize this state-of –the-art technology to discover, in unbiased fashion, the rejuvenation effects of the most widely used class of topical anti-aging agents, retinoids. In this study, we will focus on topical retinol, as it is an over-the-counter agent that has minimal side effects.

Furthermore, studies on retinol to date in humans have occurred largely in white population even though individuals of Asian descent represent the majority of the world population. The potential effects of retinol on individuals of Asian descent are uncharacterized and represent an untapped potential to explore differences in aging across ethnic groups.

While prior studies have indicated an increase in glycosaminoglycans (GAGs) and collagen after topical retinol usage (Kafi *et al.*, 2007), the true breadth of anti-aging effects including the mechanisms by which these effects are controlled has not been explored. It is possible that topical retinol has additional effects on major pathways of skin aging, such as NFkB related genes (Chang *et al.*, 2013) as well as previously unknown aging pathways. This study aims to discover the molecular basis of rejuvenation effects of retinol so that new topical agents can be identified that might mimic aspects of the retinol rejuvenation effect. We aim to do this in a Han Chinese cohort, as this is the most populous ethnic group among the East Asian population. Given the similarity in haplotype of Han Chinese with Korean and Japanese populations, these latter groups will be included as well.

Objective:

To discover new pathways of rejuvenation using topical vitamin A application on naturally aged in East Asian women.

Specific Aims:

Specific Aim 1: To discover molecular pathways of skin rejuvenation by identification of gene expression profiles after topical vitamin A in East Asian women

Specific Aim 2: To identify changes in wrinkling and biometrics associated with skin rejuvenation after topical vitamin A application in East Asian women

Specific Aim 3: To identify type and severity of adverse events associated with topical retinol usage

Materials and Methods

Formulation of topical retinol per Kafi *et al.* by combining a 41% retinol solution in 55% polysorbate 20 in sufficient proportions with fragrance-free Norwegian Formula Neutrogena Body Moisturizer (Ortho-Neutrogena Co, Los Angeles, Calif) to yield a 0.4% retinol lotion. The vehicle was similarly prepared with 55% polysorbate 20 solution in Norwegian Formula Neutrogena Body Moisturizer. There were no discernable differences in color, odor, or consistency between the active lotion with retinol and the placebo lotion control. A stability study using high-performance liquid chromatography will be performed to demonstrate that more than 90% of 0.4% retinol remained in the moisturizer 3 months after preparation. Both 0.4% retinol lotion and its vehicle were placed in dark glass containers covered with foil to eliminate transmission of UV radiation and stored at 4°C.

After Stanford Human Subjects Panel approval and written informed consent, participants will be screened for eligibility as follows:

Inclusion Criteria

Able to provide written informed consent Older group: Age between 50 and 75 years Young group: Age less than or equal to 25 years Female

Fine wrinkling score at baseline =7 or greater if in older group
All 4 grandparents of Han Chinese, Korean or Japanese descent
Willing and able to apply topical agents to inner arms
Uncontrolled medical problems including diabetes, active chemotherapy
Body mass index within normal or overweight range
No history of weight loss of >20 lbs. within past 5 years

Exclusion Criteria

Skin condition in the areas of skin biopsy that would obscure results of analysis
Topical creams or treatment to arms 2 weeks prior to study baseline visit, including
sunscreens, topical moisturizers, sunless tanners
Individuals with known hypersensitivity to retinoid class of agents
Prior anti-aging treatments to arms including retinol, microdermabrasion within 2 weeks of
baseline visit

Confidential Stanford University School of Medicine

Prior laser therapy or surgical procedure to arms
Prior radiation or other trauma (extensive burns or abrasions) to arm skin
Hormone-based therapy within 4 weeks of enrollment

Screening Visit (VISIT 1—older group only)

Only individuals fulfilling eligibility criteria will be enrolled.

As part of the screening process, clinical histories, physical examinations including vital signs, and photography of sun exposed and non sun-exposed arm will be performed. Cutometry, Raman spectroscopy (Biophotonic scanning) and transepidermal water loss will be measured.

Enrollment Visit (VISIT 2—subset of 30 participants from the older group above will be invited for this visit)

Upon enrollment into the study, patients will be instructed on proper usage topical retinol versus vehicle placebo. The placebo versus treatment arm will be clearly labeled on the subject's diary to minimize subject error. Participants will apply treatment to one arm and placebo to the other arm based on computer generated randomized assignment of left or right for the retinol. Participants are blinded to the treatment. Participants will be given a diary to record adherence to study procedures. Participants will be instructed to discontinue study if there is any itching or burning sensation that is moderate or severe and to contact study personnel immediately should this occur.

Week 12 visit (VISIT 3—the 30 participants from VISIT 2 (older group) only)

Adverse events and concomitant medication changes will be assessed and recorded. Study diary will be reviewed for adherence to study regimen. Photographs, cutometry and TEWL measurements will be taken. Two 4 mm skin biopsies will be taken at this time, one from the side with the retinol exposure and one from the side without retinol exposure after injection of a small amount of lidocaine anesthetic. Skin biopsies will be bisected and placed in either formalin for hematoxylin and eosin staining and mucin staining (for GAG), or placed into RNA later for subsequent gene expression analysis by 3'-end sequencing as described in Chang et al., 2013. Tissue will also be sent for microRNA analysis.

VISIT 1—age<25 years group only

As part of the screening process, clinical histories, physical examinations including vital signs, and photography of face, sun exposed and non sun-exposed arm skin will be performed. Cutometry, Raman spectroscopy (non invasive Biophotonic scanning) and transepidermal water loss will be measured. Photographs, cutometry and TEWL measurements will be taken. A 4 mm skin biopsies will be taken from the inner arm skin after injection of a small amount of lidocaine anesthetic. Skin biopsies will be bisected and placed in either formalin for hematoxylin and eosin staining and mucin staining (for GAG), or placed into RNA later for subsequent gene expression analysis by 3'-end sequencing as described in Chang *et al.*, 2013. Tissue will also be sent for microRNA analysis.

Statistical Considerations

This study is powered using data from Kafi et al. for the primary clinical endpoint of fine

wrinkling score as measured by semi-quantitative scale of 0 to 9. A sample size of 36 provides a power level of 0.80 in detecting a difference of 1.00 unit on mean value before and after treatment for the fine wrinkling scale, with a type I error rate of 0.05 for a 2-tailed hypothesis, assuming a standard deviation of differences to be 1.8. Assuming a dropout rate of 10%, the sample size needed is 28 subjects.

Anticipated Results

Results of photographs will be analyzed in blinded fashion by a board certified dermatologist for skin aging parameters including fine wrinkling (tertiary endpoint), dyspigmentation, and surface texture with results graded on a 9 point Likert scale per Kafi *et al.* We anticipate that there will be statistically significant differences in mean score of these parameters between pre- and post- treatment groups for both vitamin A and placebo.

Results of histology will be evaluated in blinded fashion by a dermatopathologist. Parameters of skin aging will include measurement of epidermal thickness, and density of collagen and elastin. Results from the pre- and post- treatments groups for topical vitamin A versus placebo will be compared.

Results of the cutometry and TEWL measurements will be grouped and mean and standard deviations for the older patients before and after topical vitamin A treatment will be calculated and compared to placebo. We anticipate there will be statistically significant differences in the mean scores in cutometry and TEWL measurements between treated and placebo groups.

Whole transcriptome libraries will be created from the samples stored in RNA later and sent for 3'-end sequencing at Stanford Functional Genomics Core Facility after de-identification. We have utilized this Core facility for other projects in the past with high quality results. Results will be analyzed by our bioinformatician using the methods outlined in Chang ALS *et al.*, 2013. Specifically, comparisons will be made in skin from older participants between the pre and post treatment compared to placebo. All results of interest from 3'-end sequencing will be confirmed by RT-qPCR.

We anticipate that the adverse event rate (deemed related to study agent by investigator) for participants is less than 10% and may include mild (grade 1) itching or burning.

Significance

This study will be the first broad based, unbiased investigation into the molecular basis of the anti-aging effects of topical vitamin A. This study is a high quality, well-controlled study using state-of-the art technology of 3-Seq and microRNA analysis. Our research group has established the workflow from previous larger studies in skin aging (unpublished data) and can now leverage this experience for maximal efficiency and positive results. Specifically, we would be able to compare our results to inner arm skin from females younger than 30 years whose gene expression profiles are already contained in our database.

Confidential Stanford University School of Medicine

This study will provide novel candidate gene pathways as well as confirm suspected/known genes important for skin rejuvenation in humans. This information will aid in discovery of new topical agents that might have rejuvenative capacity due to their ability to mimic aspects of the vitamin A gene expression changes.

References

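### An entry criterion on uncontrolled illness and chemotherapy stands under Inclusion Criteria without a negation, so as written it is a condition of entry

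*Combined protocol and SAP*

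**What the plan says.** The eligibility lists in Materials and Methods are introduced by the statement that "participants will be screened for eligibility as follows". Under Inclusion Criteria, between the item on willingness to apply the study lotions and the item "Body mass index within normal or overweight range", stands the line "Uncontrolled medical problems including diabetes, active chemotherapy". Two lines below it, the same list words a condition that must be absent with an explicit negative: "No history of weight loss of >20 lbs. within past 5 years".

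Where an item is meant for one age group only, the list can say so, as in "Fine wrinkling score at baseline =7 or greater if in older group". The line at issue names no group.

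The Exclusion Criteria end with "Hormone-based therapy within 4 weeks of enrollment", which is the only exclusion that concerns systemic treatment. The Screening Visit section for the older group then states: "Only individuals fulfilling eligibility criteria will be enrolled".

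**The concern.** An item under an inclusion heading is something a participant must have. This line describes states of ill health and current cancer treatment, and nothing in it reverses the sense. Taken at its word, the protocol requires what it almost certainly means to rule out.

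The stake is participant protection and the clarity of the entry rule. Both age groups have 4 mm skin biopsies under lidocaine: the older group at the Week 12 visit and the young group at its Visit 1. For the young group, screening and biopsy are described in the same visit, so the plan describes no later visit at which a misreading could be caught. This is also the only criterion in either list on general medical instability or chemotherapy. If its direction is wrong, a monitor has no other text under which such a participant would be ineligible.

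**Working it through.** No arithmetic result depends on this line, and the plan has no figure to reproduce. The check is a classification of every eligibility item, followed by a search of the remaining sections for a correction.

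**Inclusion Criteria, item by item** (the two age rules counted separately)

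| # | Item (paraphrased) | Form | Group named |
|---|---|---|---|
| 1 | Informed consent | positive | none |
| 2 | Age range, older group | positive | older |
| 3 | Age limit, young group | positive | young |
| 4 | Female sex | positive | none |
| 5 | Baseline wrinkling score | positive | older |
| 6 | Ancestry of grandparents | positive | none |
| 7 | Willing to apply the lotions | positive | none |
| 8 | Uncontrolled illness, chemotherapy | **adverse state, no negation** | none |
| 9 | Body mass index | positive | none |
| 10 | Weight loss | negated with *No* | none |

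Count: 8 positive + 1 negated + 1 un-negated adverse state = 10.

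Items that literally apply to an older participant: 10 − 1 (item 3) = 9. Items that literally apply to a young participant: 10 − 2 (items 2 and 5) = 8.

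**Exclusion Criteria**

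- Arm or biopsy-site skin: skin condition, topical products, anti-aging treatment, laser or surgery, radiation or trauma = 5.
- Retinoid hypersensitivity = 1.
- Hormone-based therapy = 1.

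Count: 5 + 1 + 1 = 7. The number naming uncontrolled disease, diabetes or chemotherapy is 0. The radiation item is limited to arm skin.

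**Other sections**

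- The screening text for both groups calls for clinical histories and physical examinations with vital signs, but gives no rule for acting on uncontrolled illness or chemotherapy.
- The Enrollment Visit, Week 12 visit, Statistical Considerations and Anticipated Results say nothing on the subject.

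**Could it touch a result?**

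- Treatment contrast: the Enrollment Visit section says "Participants will apply treatment to one arm and placebo to the other arm", so a person's general health is common to both sides of the comparison, which largely protects it.
- Adverse events: the anticipated rate in Anticipated Results counts only events judged related to the study agent.
- Gene expression: the specified comparison is in older participants, and no analysis of the young-group samples is defined.

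The effect is therefore confined to who may enter.

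**The case against.** The strongest objection is that the error reveals itself. A study of naturally aged skin that also restricts body mass index and past weight loss does not plausibly seek women with uncontrolled disease. Any reader would reverse the line, no endpoint, sample size, randomisation or analysis depends on it, and it is at most an editorial slip. Most of this stands: a slip is the likely explanation and the practical effect is probably small. It does not remove the need for correction, because an eligibility rule should not rely on staff applying the opposite of its wording.

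A second objection is that the missing group qualifier does not show that the line was meant for both groups. The willingness item just above it also has no qualifier, yet the young group is never described as applying a lotion. In addition, the sentence requiring the criteria to be fulfilled sits under the older group's screening visit. The qualifier argument is indeed weak on its own, and the count of 8 for a young participant is literal: without the willingness item it would be 8 − 1 = 7. The both-groups reading rests instead on the lead-in sentence, which precedes the whole list.

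Third, ethics approval comes before screening, and histories and examinations are taken in both groups, so unnoticed enrolment through this line is less plausible. The documents also do not say that these conditions raise biopsy risk. Both points are fair, and they limit the participant-protection argument to the absence of a written safeguard.

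Finally, a *No* could have been lost when the text was read from PDF, and the layout of this list is visibly altered, with several criteria run together on one line. This cannot be fully ruled out. It is unlikely, since the line sits between intact items, no gap is marked and the *No* two lines below survived.

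**Conclusion.** The concern holds. The line is wrong as written: it is an un-negated adverse condition under an inclusion heading, it operates as an entry rule, and nothing else in the document corrects it. It should be fixed, although the practical effect is likely small. The number of participants affected is not stated, and it is zero if the line was applied as an exclusion throughout. The item counts describe the extent of the problem in the text, not a consequence.

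Two assumptions underlie this. One is that the extracted text matches the source document, which a look at the source would settle. The other is that the slip is one of drafting, which is an inference from the wording and its neighbours. The finding is limited to this one line; the rest of the list does not read backwards.

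**What to change.** Reconcile the line with its heading and with the Exclusion Criteria, so that its direction is unambiguous and matches what the sponsor intended. In the same edit, make clear whether the word *uncontrolled* qualifies diabetes, which the present wording leaves open, and state whether the criterion applies to both age groups. Then confirm that screening in both groups was done on that basis.

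The cost is a one-line protocol correction and a check of screening practice. If the line was already treated as an exclusion, recruitment does not change. The sample size and the analysis are unaffected.

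### The participant's own diary is to show which arm is placebo and which is treatment, yet participants are said to be blinded

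*Combined protocol and SAP*

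**What the plan says.** The relevant text is almost all in one paragraph of the combined protocol and SAP, under Enrollment Visit (VISIT 2). In order, it says:

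- At enrollment, "patients will be instructed on proper usage topical retinol versus vehicle placebo".
- On the diary, "The placebo versus treatment arm will be clearly labeled"; the reason given is to reduce mistakes by the participant.
- One arm receives retinol and the other vehicle, "based on computer generated randomized assignment of left or right for the retinol".
- "Participants are blinded to the treatment".
- The participant is given the diary and records adherence in it.

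Elsewhere, Materials and Methods describes a matched vehicle: "There were no discernable differences in color, odor, or consistency between the active lotion with retinol and the placebo lotion control". The containers are foil-covered dark glass, a measure against UV exposure; no labelling scheme is given. Under Anticipated Results, "Results of photographs will be analyzed in blinded fashion by a board certified dermatologist", and histology is also read blinded. The same section says that cutometry and TEWL results "before and after topical vitamin A treatment will be calculated and compared to placebo". Specific Aim 3 is "To identify type and severity of adverse events associated with topical retinol usage".

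**The concern.** A diary that the participant holds, and that identifies the placebo arm and the treatment arm, discloses the allocation. The protocol claims participant blinding and, in the same paragraph, gives an instruction that would remove it.

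The design makes this matter more than it might in a parallel-group trial. Both arms belong to one person, who applies both lotions herself, and no visit is described between enrollment and Week 12. If she knows the active side, she may apply that lotion more carefully, or use other products on one side only. Any such imbalance becomes part of the within-person contrast on which the clinical, instrumental and gene-expression comparisons with placebo rest.

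The adverse-event aim is exposed more directly. The events the protocol anticipates are itching and burning, which are sensations reported by the participant, and knowing the active side can change what is reported for which arm. Participants are also told to stop if such a sensation is moderate or severe, so biased reporting could affect retention as well.

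**Working it through.** **1. Consistency of the text.** The plan has no figure to reproduce on this point, so the check is a reading of every statement on blinding, labelling, coding or masking.

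| Question | What the documents give |
|---|---|
| What does the diary show? | Placebo arm versus treatment arm, clearly labelled (Enrollment Visit) |
| Who holds the diary? | The participant (Enrollment Visit) |
| Is the participant blinded? | Yes, stated outright (Enrollment Visit) |
| Is a coded or neutral label described? | No, neither for the diary nor for the containers |
| Who holds the allocation list? | Not stated |
| Do the instructions to participants use coded names? | None mentioned; the text refers to retinol versus vehicle |
| Can the lotions be told apart? | No; they are matched (Materials and Methods) |
| Who else is blinded? | Photograph and histology readers (Anticipated Results) |

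The first three rows conflict, and nothing in the remaining rows resolves the conflict. The matched vehicle conceals identity only if no label reveals it.

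**2. Is the treatment identity needed for the label's stated purpose?** The purpose is to stop participants mixing up the arms. Allocation is by left or right, so a container marked with the side it belongs to prevents a mix-up completely. Naming the treatment adds nothing to that.

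**3. Illustration of what a bias would do.** The documents do not allow the bias to be estimated. To show scale only, suppose there is no true retinol effect and knowledge of the side produces a between-arm difference of *b* units on the wrinkling scale.

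Inputs:
- *n* = 30 × (1 − 0.10) = 27 completers. The 30 is from the Enrollment Visit section and the 10% dropout from Statistical Considerations; combining them is an assumption.
- SD = 1.8, from Statistical Considerations. It is stated there for before/after differences and is borrowed here because no between-arm SD is given. The values 1.2 and 2.4 are assumed as a range.
- *b* = 0.10, 0.25 and 0.50, all assumed.
- Two-sided paired t-test, alpha 0.05, 26 degrees of freedom, critical value 2.056.

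The noncentrality is δ = *b*√*n* / SD. For *b* = 0.25 and SD 1.8, δ = 0.25 × 5.196 / 1.8 = 0.722. The chance of a significant result is P(|T| > 2.056), with T noncentral t on 26 degrees of freedom.

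| *b* | SD 1.2 | SD 1.8 | SD 2.4 |
|---|---|---|---|
| 0 | 0.050 | 0.050 | 0.050 |
| 0.10 | 0.070 | 0.059 | 0.055 |
| 0.25 | 0.181 | 0.107 | 0.082 |
| 0.50 | 0.550 | 0.285 | 0.181 |

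Under these assumptions, a bias of a quarter of a unit at SD 1.8 roughly doubles the nominal 5% false-positive rate. The finding does not depend on this table.

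**The case against.** The strongest reply is that the authors meant a coded or side label. The protocol states blinding outright, describes a matched vehicle, and says the label is there to reduce participant error; together these fit an under-specified label at least as well as a plan to disclose the allocation. That is fair, and it means actual unblinding cannot be asserted. It does not cure the text. Staff preparing diaries would follow the sentence as it stands, and the documents give them no other instruction.

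A second reply is that most outcomes are insulated: photographs and histology are read blinded, gene expression comes from sequencing, and cutometry and TEWL are instrument readings. This holds for reader bias, and the wrinkling grade is not directly unblinded by the diary. It does not hold for real differences in how the two arms were treated, which any measurement would pick up. The Week 12 review of adherence and concomitant medication might detect some of this but would not prevent it. Participant-reported itching and burning have no such protection.

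A third reply is that the illustrative figures rest on invented biases, a borrowed SD and a constructed number of completers. That stands. They show scale only and should carry no weight in judging severity.

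**Conclusion.** The concern holds. As written, the Enrollment Visit section contradicts itself on participant blinding, and nothing elsewhere in the documents resolves it. This is an instruction that defeats a stated design feature if it is followed, which is more serious than a missing detail.

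It reaches all 30 planned participants. The size of any resulting bias is unknown and cannot be derived from the documents. The conclusion rests on the literal wording and on the absence of any described code. It allows that a coded label may have been intended, in which case the text still has to say so. The point must be fixed before diaries are issued, because unblinding that has occurred cannot be repaired in the analysis.

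**What to change.** Replace the diary-label sentence with text such as:

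> *Containers and diary will be labelled only LEFT ARM and RIGHT ARM (or coded A/B). The retinol side will be held in the randomization list and not shown to the participant.*

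This still prevents mix-ups between arms. Two details help it work. If an A/B code is chosen, its meaning should vary between participants, so that one disclosure does not unblind everyone. The sentence on instructing patients should use the same neutral labels.

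The cost is the wording on diary and containers, and keeping the list from participants. Sample size, visits and analysis do not change.

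Masking the staff who take the Week 12 measurements is a separate, optional matter. It would cost more, because it needs a code holder and biopsy specimens labelled by left or right; the Week 12 section at present describes biopsies by retinol exposure.

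### Mild itching or burning that settles before Week 12 is likely to be under-recorded for Aim 3: the diary is described for adherence only, and adverse events are assessed once, at Week 12

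*Combined protocol and SAP*

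**What the plan says.** All references are to the combined protocol and SAP.

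- **Specific Aims.** Aim 3 is "To identify type and severity of adverse events associated with topical retinol usage".
- **Enrollment Visit (Visit 2).** On the diary: "Participants will be given a diary to record adherence to study procedures". The same section says that the diary shows which arm receives active lotion and which placebo, and that participants are blinded. The instruction to stop and get in touch applies to "any itching or burning sensation that is moderate or severe and to contact study personnel immediately should this occur".
- **Week 12 visit (Visit 3).** "Adverse events and concomitant medication changes will be assessed and recorded". The diary is mentioned again: "Study diary will be reviewed for adherence to study regimen".
- **Anticipated Results.** The rate of events judged related by the investigator is expected to be "less than 10% and may include mild (grade 1) itching or burning".

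No visit, telephone call, symptom log or symptom scale is described between Visit 2 and Week 12.

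**The concern.** The only reaction the plan names in its forecast is mild, and mild reactions fall below the threshold at which participants are asked to make contact. The diary is the one instrument in the participant's hands for those 12 weeks, and both descriptions of its use concern adherence. A mild reaction that appears early and then settles has no stated route into the data except memory at one visit, or an unprompted report.

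Two features of Aim 3 are exposed.

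- **Severity.** Moderate and severe reactions prompt contact when they occur and mild ones do not, so the severity mix leans toward the former.
- **Attribution.** Each woman has retinol on one arm and vehicle on the other. Linking a reaction to retinol requires knowing which arm reacted, and the plan does not say that this is noted when the reaction occurs.

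A low recorded rate could also be taken as support for the forecast of under 10% when it partly reflects how events were collected. Mild events missed during treatment cannot be reliably reconstructed later.

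**Working it through.** **1. Routes into the data, as written**

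| Reaction | Route before Week 12 | Route at Week 12 |
|---|---|---|
| Moderate or severe itching or burning | Requested contact | Adverse event assessment |
| Mild, still present at Week 12 | None requested | Direct assessment |
| Mild, settled before Week 12 | None requested | Memory only |

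The gap is the third row.

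**2. Direction of the bias**

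Let p be the true proportion of women with a mild reaction and s the share of those reactions that is recorded.

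- The recorded rate is q = s × p, which is below p whenever s < 1.
- With m mild and h moderate or severe reactions, and the latter fully recorded, the mild share falls from m/(m + h) to sm/(sm + h). Severity is tilted upward.
- If s is the same for both arms, the recorded retinol-minus-vehicle difference also shrinks by the factor s.

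**3. Size: illustration on assumed values**

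The plan gives its figure of under 10% as an expectation without a derivation, so there is nothing to reproduce.

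Inputs from the plan:
- N = 30 women (Enrollment Visit).
- 10% threshold (Anticipated Results). Below 10% of 30 means 0, 1 or 2 women.

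Inputs assumed, because the documents give neither:
- p = 15% or 20%.
- s = 40%, 60% or 100%.

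I also assume that all related events are mild, that each woman counts once, and that women are independent.

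Formula: P(X ≤ 2) = (1 − q)^30 + 30q(1 − q)^29 + 435q²(1 − q)^28.

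Worked case, p = 20% and s = 40%: q = 0.08, and 0.082 + 0.214 + 0.270 = 0.565 (from unrounded terms).

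| True rate p | Capture s | Recorded rate q | Expected count of 30 | P(fewer than 3) |
|---|---|---|---|---|
| 15% | 100% | 15% | 4.5 | 0.151 |
| 15% | 60% | 9% | 2.7 | 0.486 |
| 15% | 40% | 6% | 1.8 | 0.732 |
| 20% | 100% | 20% | 6.0 | 0.044 |
| 20% | 60% | 12% | 3.6 | 0.285 |
| 20% | 40% | 8% | 2.4 | 0.565 |

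**4. Sensitivity**

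- *Completers only.* With the plan's 10% dropout, 30 × 0.9 = 27. Below 10% still means at most 2 women. At 100%, 60% and 40% capture the probabilities are 0.207, 0.557 and 0.781 for p = 15%, and 0.072, 0.355 and 0.632 for p = 20%.
- *True rate inside the forecast.* At p = 8% with N = 30, P(fewer than 3) is already 0.565 with full capture. The forecast is then true, and a result under 10% misleads nobody. The count still falls, from 30 × 0.08 = 2.4 to 2.4 × 0.4 = 0.96 at 40% capture.

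**The case against.** A reader might infer that mild reactions are captured by recall alone and that Aim 3 is certain to be undercounted. The documents do not support that. A mild reaction still present at Week 12 can be assessed directly. The moderate-or-severe wording is an instruction on stopping and making contact, and it does not bar women from reporting milder symptoms. The diary form is not in the document, so a symptom field cannot be excluded. This limits the claim to mild reactions that settle early, and to likely under-recording.

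A reader might also take a contrast such as 0.565 against 0.044 as the size of the problem. It is not. The capture shares have no source in the documents, and a true rate of 20% is at least double the plan's own forecast. That forecast covers all events judged related, not only mild itching or burning. It is not a hypothesis, endpoint or stopping boundary, and no decision rests on it. Aim 3 is descriptive, in 30 women. All of this stands, so the table shows sensitivity only.

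The last objection concerns the remedy. If the diary literally names the active and placebo arms, symptoms self-reported by arm would be open to expectation, and a recall bias would be exchanged for a reporting bias. Repeated prompting can also raise reporting, the plan defines no severity scale, and the burden is more than a column or two. These objections also stand, and they shape the fix. They do not remove the gap.

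**Conclusion.** The point holds in limited form. Followed as written, the plan is likely to under-record mild itching or burning that settles before Week 12. The direction follows from the text: the recorded rate is lowered and the severity mix is tilted upward. It assumes only that some settled mild reactions go unreported at Week 12 and that stronger ones do prompt contact.

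The size is unknown. If the true rate were 15% to 20% and 40% to 60% of mild reactions were recorded, the chance of a result under 10% would be 0.285 to 0.732, against 0.044 to 0.151 with full capture. If the true rate is below 10%, the forecast is right and the only harm is a lower count. The primary clinical endpoint is not affected. This is a worthwhile, inexpensive improvement to data collection.

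**What to change.** Replace the diary sentence under the Enrollment Visit with wording such as:

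> Participants will note in the diary, with the date and separately for the left and right arm, each application and any itching, burning or other skin reaction, rated mild, moderate or severe.

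Under the Week 12 visit, state that adverse events are taken from the diary as well as from interview, and are recorded by arm.

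Label the diary by left/right or by coded bottle, not as placebo versus treatment, so that symptom reports stay blinded as the Enrollment Visit section intends. If the form already has a symptom field, saying so in the protocol is enough, provided that the labelling is settled.

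The instruction on stopping and contacting staff is not changed.

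**Cost.** Some added participant burden and data entry; the total cannot be calculated because no application frequency is stated. The recorded mild-event rate is likely to be higher, partly because of prompting. The vehicle arm, prompted in the same way, is the comparison for that. The change should be in place before the first participant receives a diary.
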